7.3 Study Purpose/Rationale

Outcome for children with recurrent malignant glioma, especially GBM, is dismal with currently available therapeutic modalities. The blood-tumor barrier is a major impediment to therapy and approaches that bypass this barrier may be required. Oncolytic immunotherapy is a promising biologic approach to treatment that not only induces viral mediated tumor destruction, but also harnesses a complex immune response that can serve in disease control. The genetically engineered oncolytic PV (PVSRIPO) has tropism for tumor cells by virtue of expression of CD155 in tumor cells. To facilitate concentration of the therapeutic agent at the tumor site, while minimizing systemic exposure, PVSRIPO will be delivered directly into the tumor. Significant pre-clinical anti-tumor activity of PVSRIPO has been observed in several rodent tumor models and *in vitro*. PVSRIPO was devoid of neuropathogenicity when injected into the thalamus of non-human primates even at doses as high as 5×10^9 TCID. Also, the phase I trial of PVSRIPO in adults with recurrent WHO grade IV malignant glioma still in the follow-up phase did not yield evidence of viral encephalomyelitis, poliomyelitis or meningitis with a proportion of patients enjoying prolonged disease survival up to 58+ months. The main toxicity attributable to PVSRIPO has been post-treatment peri-tumoral inflammation that has required prolonged steroid therapy and/or low dose bevacizumab to control edema. CD155 expression in pediatric GBM has been confirmed in 10 tumor samples. Therefore, a phase Ib study should be conducted in this high-risk pediatric population to evaluate feasibility, safety, and preliminary evidence of efficacy of the selected adult dose (5×10^7 TCID).

The Food and Drug Administration (FDA) recommended that the pediatric trial initially enroll patients 12 years of age and older and up to and including 18 years of age. We are including a number of WHO grade III and IV malignant brain tumor histologies and tumor locations in this trial. Specifically, eligible patients may include patients with recurrent WHO Grade III gliomas, such as anaplastic astrocytoma, anaplastic oligoastrocytoma, anaplastic oligodendrogloma, anaplastic pleomorphic xanthoastrocytoma, or ependymoma, as well as patients with WHO Grade IV gliomas, including glioblastoma or gliosarcoma. CD155 is avidly expressed in medulloblastoma, atypical teratoid rhabdoid tumor (ATRT), and embryonal tumors ²⁶, so these histologies will be included here as well.

Given that the incidence of embryonal tumors, ependymoma, and glioma peaks at ages lower than the initial eligible age for this clinical trial (≥ 12 years old), the study has experienced relative challenges to enrollment during its first two years. The incidence of the aforementioned tumor types is higher in younger children approximately 5 to 9 years of age and then continuously falls after 9 years old to a nadir in early adulthood ^{27,28}. In addition, the biology of brains in children aged 4 to 11 and the biology of the predominant types of brain tumors seen in this age range (i.e., glioma, ependymoma, and medulloblastoma) are similar to that of children who are 12 and over ¹. Tumors in children younger than 4 years old tend to have different genotypes and thus behave differently than tumors in children older than 4 years old ¹. There are currently active pediatric clinical trials in the US investigating the use of different oncolytic viruses, such as herpes simplex virus-1 (HSV-1) (NCT03911388 and NCT02451845) and a modified measles virus (NCT02962167), in a similar pediatric population. These trials also deliver the oncolytic virus via intratumoral administration and

include a population of children ranging in age from 3 to 18 years old in the case of aforementioned HSV-1 trial and children and adults ranging in age from 1 to 39 years old in the case of the modified measles virus.

8 OBJECTIVES AND ENDPOINTS

Table 1. Objectives and Endpoints

	Objective	Endpoint	Analysis
Primary	Confirm the safety of the selected dose of PVSRIPO when delivered intracerebrally by convection-enhanced delivery (CED) in children with recurrent Grade III or IV MG	Percentage of patients that experience unacceptable toxicity during the 14-day period post-PVSRIPO treatment. Proportion of patients who require low-dose bevacizumab or steroid treatment due to an inflammatory reaction secondary to an immune response to PVSRIPO treatment will be calculated.	See Section 15.4
Secondary	Estimate Overall Survival (OS) in children with recurrent WHO Grade III and IV malignant glioma treated with a single dose of PVSRIPO	Proportion of patients alive 2 years after PVSRIPO treatment	See Section 15.5

Exploratory	Describe changes visualized on imaging due to intratumoral inoculation of PVSRIPO	Description of imaging changes	See Section 15.6
Other Exploratory	Describe changes in tumor volume visualized on imaging after intratumoral inoculation of PVSRIPO	Change from baseline in tumor volume based on imaging	See Section 15.7
Other Exploratory	Assess immunologic responses in peripheral blood and in serum	Change from baseline in immune function	See Section 15.7
Other Exploratory	Identify genetic predictors of response or failure of response to treatment with PVSRIPO	Identification of genetic markers as predictors of response	See Section 15.7

9 INVESTIGATIONAL PLAN

9.1 Study Design

9.1.1 Catheter Implantation

Systemic delivery of high molecular weight therapeutic agents to brain tumors is limited by the blood-brain barrier and increased interstitial pressure within the tumor. PV CNS invasion after intravenous administration via trans-endothelial passage is inefficient ²⁹. Intratumoral delivery bypasses these physiologic barriers and concentrates the therapeutic agent at the tumor site while minimizing systemic exposure. Therefore, PVSRIPO will be delivered directly into the tumor. A stereotactic biopsy will be performed prior to virus administration for frozen section confirmation of viable tumor and further analysis (see Section 9.1.4 below). The biopsy needle will be placed with stereotactic guidance by a Cosman-Robert-Wells, MRI-compatible, stereotactic head frame or a similar frameless device. Collection of biopsy tissue for pathologic diagnosis will be performed under traditionally accepted conditions according to standard of care. Up to three additional core biopsies will be obtained for molecular genetic testing as described in section 9.1.4.

If this biopsy does not confirm recurrent tumor, the subject will be withdrawn from the study.

Immediately following the stereotactically-guided tumor biopsy, a catheter [VYGON PIC-030 (Sophysa, Inc.; Crown Point, IN)] will be implanted in the operating room at a site the same or different from that used for the biopsy using sterile techniques under general anesthesia. Implantation will occur at a coordinate selected by the operating surgeon with the assistance of the clinically-approved iPlan Flow (BrainLAB). The catheter will be implanted at least 1 cm away from the ventricles. Based on our experience, a tumor \leq 1cm from the ventricles can safely and feasibly have a catheter placed \geq 1cm from the ventricles while minimizing the possibility of infusate entering the ventricles. The catheter will be tunneled beneath the scalp for a distance of at least 5 cm to aid in the prevention of infection. A CT scan may be used to confirm catheter placement post-operatively.

9.1.2 Agent Infusion

Refer to the study Investigational Product Handling Plan (IPHP) for additional details regarding the infusate preparation and infusion procedure. The entire volume of the prepared infusate will be provided in a sterile infusion syringe by the investigational pharmacist and connected to the catheter under sterile conditions in the Pediatric Intensive Care Unit (PICU) just prior to beginning of infusion. Due to the complexity of scheduling all of the necessary components for the infusion (operating room time, pharmacy time, and radiology appointments), a +1 day window has been built into the study for the study drug infusion. This means that the infusion is allowed to start the following day after the

biopsy/catheter placement. This will still be considered “day 0” with regard to the protocol and the timing of the subsequent events. At the time of virus injection, emergency drugs, including epinephrine and diphenhydramine will be available and the neurologic status, oxygen saturation, and cardiac rhythm will be monitored. Drug infusion will occur in the PICU so that all other emergency facilities will be available. Patients will be treated with a prophylactic antibiotic prior to biopsy and catheter insertion per DUHS neurosurgical standard practice.

Based on our own experience, previously published reports ⁵ and IRB- and FDA-approved trials using similar infusion techniques, patients will be infused at a rate of 0.5mL/hr. A Medfusion 3500 or 3010a infusion pump will be pre-programmed to a delivery rate of 500 μ L/hr. The infusate will be loaded in a syringe into the syringe pump at the initial onset to avoid any interruptions in the infusion. The total amount of the infusate delivered to the patient will be 3 mL. The infusion pump will be programmed for delivery of the 3.0mL at a rate of 0.5ml/hr, over approximately 6.5 hours. The catheter itself (30 cm length, 1 mm interior diameter) cannot be preloaded with virus suspension. To account for this catheter dead space, the pump will be stopped when the delivered amount is between 3.125 to 3.250 mL. The infusion will be performed using a Medfusion 3500 or 3010a (Smiths Medical ASK, Inc., Minneapolis, MN) syringe infusion pump. The catheter will be removed in the PICU following the post-PVSRIPo infusion MRI. No sedation is required for catheter removal.

The infusion catheter (PIC 030) and infusion tubing (PIT 400) are manufactured by Sophysa, Inc. (Crown Point, IN). The Infusion Catheter Kit is a 30 cm clear, open-ended catheter (1.0 mm ID/2.0 mm OD) with 1 cm markings for 20 cm. The catheter comes with a 30 cm stainless steel stylet, a barbed female luer lock with cap and a stainless steel trocar. The Infusion Tubing Kit consists of a 3-way stopcock connector with air filter, 4 m of microbore tubing with antisiphon valve, a red, vented cap and a white luer lock cap. The catheter products are packaged sterile and non-pyrogenic and are intended for single (one-time) use only.

Acute Reaction. Any acute reaction symptoms determined to be an acute reaction to the study drug will be managed by the PICU and pediatric neurosurgical teams.

9.1.3 Gadolinium Distribution Quantitation (applies only to patients treated prior to October 31, 2019)

This gadolinium tracking MRI procedure has been removed and applies only to patients treated prior to October 31, 2019. Magnevist® is no longer being manufactured and, as such, is no longer being included in the infusate.

MRI imaging, within 4 hours of the completion of infusion, was registered to define the shape and position of the contrast agent distribution relative to the patient’s brain anatomy in patients treated prior to October 31, 2019. Because enrollment criteria for these patients was limited to patients aged \geq 12 years old, sedation was not required for the MRI. While gadolinium-diethylene triamine pentaacetic acid (Gd-DTPA) is a widely available MRI contrast agent, there has been speculation that its small molecular weight (938 Dalton) could limit its ability to predict the distribution of the larger molecules typically infused therapeutically with CED [reviewed in Reardon et al., 2011 ³⁰]. Development of large molecule tracers labeled with gadolinium (Gd) has been problematic, but it has been stipulated that infusion of low molecular weight Gd-DTPA can predict the distribution of larger molecules by systematic post-infusion manipulation of the images based on theoretical differences in the predicted distribution of the Gd-DTPA and the therapeutic drug being infused ³¹. This has been confirmed by simultaneously infusing a patient with a supratentorial recurrent malignant glioma with an epidermal growth factor receptor (variant III) (EGFRvIII)-targeted immunotoxin in combination with ¹²⁴I-human serum albumin (HSA) [to permit positron emission tomography (PET) imaging] and Gd-DTPA. Gd-DTPA co-infusion provided direct information about the distribution of large molecules with high resolution ³¹. In combination with fluid-attenuated inversion recovery (FLAIR) imaging, Gd-DTPA co-infusion provides additional information about leak into cerebrospinal fluid spaces and resection cavities ³².

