10.4 Dispensing and Preparation

Refer to the study IPHP for details of PVSRIP0 dispensing and preparation. In brief, preparation of PVSRIP0 will occur in a biosafety cabinet designated for viral vector agents. For thawing, vials containing PVSRIP0 should be removed from the -80°C freezer and kept at room temperature. PVSRIP0 contained in the clinically intended delivery apparatus is stable at room temperature for 18 hours, but should be used as soon as possible. The vials contain a clear, aqueous solution, which does not require reconstitution. **Do not thaw with heating devices (waterbath, heat-block) as a loss of potency may result. Do not expose vials to UV-light (in biosafety cabinets), as a loss of potency will result.** Thawed vials should not be re-frozen/thawed for later use, because potency may be lost. Thawed vials/study syringes containing PVSRIP0, which were kept for >48 hrs at 4°C prior to the infusion procedure, should be discarded, as a loss of potency may have occurred. Thawed vials/study syringes containing PVSRIP0, which were exposed for >12 hrs at room temperature prior to the infusion procedure, shall be discarded as a loss of potency may have occurred. For aliquot preparation, the agent will be thawed slowly on ice ($\sim 4^{\circ}\text{C}$) and kept at that temperature. The vials take approximately 30 minutes to thaw. The manufacturer will provide the study agent's potency (as tissue culture infectious doses) and will also supply the appropriate vehicle for aliquot preparation. Aliquot preparation will occur in the ICS. All handling of the study agent will occur in a biosafety cabinet or a similarly contained environment.

Any materials in contact with the study agent, e.g. syringes, vials, etc., will be disposed of as biological waste. The final desired aliquot of the study agent infuse will be prepared at the intended volume sufficient for priming the infusion tubing and for infusion. . The capped infusion syringe containing infuse (and primed infusion tubing if primed in pharmacy) will be transported to the study site in a 'ziplock' bag placed in a portable cooler or similarly contained transport device with a frozen ice block/ice pack, in order to maintain a temperature of approximately 4°C . No need to monitor the temperature during transport to the bedside.

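### At the stated 30 cm catheter length, stopping the pump at the 3.125 mL lower limit delivers 2.889 mL, not the stated 3 mL

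*Combined protocol and SAP*

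**What the plan says.** Section 9.1.2 gives the target volume: "The total amount of the infusate delivered to the patient will be 3 mL". It describes the catheter: "The catheter itself (30 cm length, 1 mm interior diameter) cannot be preloaded with virus suspension". The stopping rule comes next and refers back to that catheter: "To account for this catheter dead space, the pump will be stopped when the delivered amount is between 3.125 to 3.250 mL". The kit description later in the same section repeats the dimensions: "The Infusion Catheter Kit is a 30 cm clear, open-ended catheter (1.0 mm ID/2.0 mm OD) with 1 cm markings for 20 cm".

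The pump setting reads: "The infusion pump will be programmed for delivery of the 3.0mL at a rate of 0.5ml/hr, over approximately 6.5 hours". Section 5.3 gives the same 3 mL and 0.5 mL/hr, with a duration of 6 hours 30 minutes.

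Section 10.4 says that the aliquot is "prepared at the intended volume sufficient for priming the infusion tubing and for infusion". With the tubing primed, the catheter lumen is the dead space that the stopping rule has to cover.

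Two other lengths appear, and neither is a working length of the catheter. The 5 cm in Section 9.1.1 is a minimum tunnel distance under the scalp, and the 20 cm in the kit description is the marked portion. Section 9.1.2 refers to an Investigational Product Handling Plan for further detail; that plan is not among the documents reviewed.

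**The concern.** The stop window exists so that the patient receives 3 mL although some fluid stays behind in the catheter. Its lower limit allows 0.125 mL for this, which is about 53% of what the described lumen holds (0.125/0.2356). An operator can therefore follow the instruction exactly and still deliver less than the volume stated in the same section.

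This is an operative dosing instruction for a single intracerebral infusion, in a trial whose primary objective is to confirm the safety of one selected dose. The stated volume and the rule meant to achieve it should agree.

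**Working it through.** **Inputs.** Target volume 3 mL; catheter length 30 cm; internal diameter 1 mm (radius 0.05 cm); stops 3.125 and 3.250 mL; rate 0.5 mL/hr (all Section 9.1.2); duration 6 h 30 min (Section 5.3). I take the delivered amount in the stopping rule to be the volume pumped, with primed tubing, no extra connector volume and plug flow.

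**Step 1: dead space.** Lumen area = π × 0.05² = 0.00785 cm², so each cm of catheter holds 0.00785 mL. At 30 cm the dead space is 0.2356 mL.

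**Step 2: stop needed for 3 mL.** 3 + 0.2356 = 3.2356 mL.

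**Step 3: reproduce the plan's figure.** At the upper stop, 3.250 − 0.2356 = 3.014 mL, which is +0.5% against 3 mL. The time is 3.250/0.5 = 6.5 h, as Section 5.3 states. The upper stop therefore reproduces both the volume and the duration.

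**Step 4: lower stop.** 3.125 − 0.2356 = 2.889 mL. The shortfall is 0.111 mL, or −3.7%. The time is 3.125/0.5 = 6.25 h.

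**Step 5: what length would each stop fit?** Lower: 0.125/0.00785 = 15.9 cm. Upper: 0.250/0.00785 = 31.8 cm. The window as written fits catheters from about 16 to 32 cm.

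**Step 6: sensitivity to length.** The lengths below 30 cm are assumptions.

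| Length (cm) | Dead space (mL) | Delivered at 3.125 (mL) | Delivered at 3.250 (mL) |
|---|---|---|---|
| 30 | 0.236 | 2.889 | 3.014 |
| 25 | 0.196 | 2.929 | 3.054 |
| 20 | 0.157 | 2.968 | 3.093 |
| 15.9 | 0.125 | 3.000 | 3.125 |

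**Step 7: sensitivity to rounding of the diameter.** If the true internal diameter lies between 0.95 and 1.049 mm, the lower stop at 30 cm delivers 2.912 to 2.866 mL, so rounding does not close the gap. The upper stop then delivers 3.037 to 2.991 mL.

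**The case against.** The strongest reply is that the window may be deliberate. The kit lists "a barbed female luer lock with cap and a stainless steel trocar" among its separate items, and Section 9.1.1 says "The catheter will be tunneled beneath the scalp for a distance of at least 5 cm". A surgeon might shorten the catheter, and a range covering about 16 to 32 cm would then be sensible. The handling plan, which is not available here, may say so. This part stands: the lower limit cannot be shown to be wrong for a shortened catheter. But the documents do not mention trimming, and Section 9.1.2 ties the window to the dead space of a 30 cm catheter. If a shorter length is meant, the section needs to state it.

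A second reply is that a fixed 3.25 mL stop would over-deliver through a short catheter: 3.125 mL at 15.9 cm, or +4.2%. That is true, but the present window already permits that stop, so fixing it there creates no exposure that is not already allowed.

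A third is that 2.889 mL rounds to 3 mL. The stops are given to 0.001 mL, so whole-millilitre rounding is not the precision that the section works to.

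A fourth is that the consequence is slight. This stands. Section 7.2.6 sees no clinically important difference between 5×10^7 and 1×10^7 TCID50, a five-fold gap, and Section 9.4 counts a patient who received any dose as evaluable.

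Three stronger readings are tempting, and the documents do not support them:

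- A reader might infer that most infusions fall short, because most of the window lies below 3.236 mL. Nothing says where in the window stops occur, and the stated durations point towards its upper end.
- A reader might infer that the pump is set to push only 3.0 mL. At 0.5 mL/hr that would take 6.0 h, whereas the same sentence gives about 6.5 h and the stopping rule soon after gives a larger volume. The 3.0 mL is the amount meant to reach the patient.
- A reader might infer that the stated times rule out the lower stop. Section 9.1.2 says only approximately 6.5 hours, which admits 6.25 h. Section 5.3 matches the upper stop exactly, and that stop is inside the window.

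**Conclusion.** The point holds as a minor inconsistency within Section 9.1.2. For the catheter that the section describes, only stops of about 3.236 mL or more deliver 3 mL. The lower limit delivers 2.889 mL, a shortfall of at most 3.7% at the nominal dimensions, and the upper limit is right. If the 3 mL carries the full 5×10^7 TCID50 (an assumption, since no concentration is given), the lower stop corresponds to 5×10^7 × 2.889/3, or about 4.82×10^7.

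The result rests on the full 30 cm being used and on the primed-tubing and plug-flow assumptions in the working; unprimed connector volume would enlarge the shortfall. The endpoints, the analysis sets and the monitoring rules in Table 4 are unaffected.

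**What to change.** For a full-length catheter, replace the window in Section 9.1.2 with a single stop at 3.25 mL, which agrees with 6.5 h at 0.5 mL/hr. Alternatively, raise the lower limit to about 3.24 mL (3.24 − 0.2356 = 3.004 mL delivered). That leaves only 0.01 mL, or 0.01/0.5 h = 1.2 minutes, before the upper limit, so the single stop is simpler to run.

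If catheters are shortened in practice, say so and set the stop at 3.0 mL plus 0.00785 mL per cm of catheter actually used: for example, 3.157 mL at 20 cm and 3.236 mL at 30 cm.

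For a full-length catheter the cost is a change of wording in one section, with the handling plan brought into line if it repeats the window. If catheters are shortened, the length used must also be known when the stop is set. The analysis does not change.

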9.1.4 Biopsy Sampling and Analyses

Biopsy material will be obtained from tumor tissue prior to virus administration. This tissue material will be subjected to routine histology to confirm tumor recurrence by the study neuropathologist, Dr. [name] or his designate.

Molecular genetic tests will also be conducted on extracts of tumor cells from the protocol-specified biopsy prior to PVSRIPO infusion. After acquiring sufficient tissue for standard clinical pathologic testing, up to three additional core biopsies will be obtained, if possible. These additional core biopsies will be frozen in optimal cutting temperature (OCT) fixative and kept at liquid nitrogen temperature. They will be used for genetic analysis, including full genome or full exome sequencing as well as other molecular genetic testing. The goal of these molecular genetic tests is to identify genetic predictors of response or failure of response to treatment with PVSRIPO. The molecular genetic testing will include, but is not limited to, DNA sequencing, gene amplification, and gene expression.

The goal of these molecular genetic tests is to identify genetic predictors of response or failure of response to treatment with PVSRIPO. The amount of tissue required for this testing should be sufficient to yield a minimum of one microgram of DNA.

Following PVSRIPO administration and outside the context of this protocol, patients may undergo tumor resection or biopsy as medically indicated for reasons not part of the investigative protocol. Should subjects have a resection at a later time, we will request samples of this resected tissue for tissue analysis. If subjects agree to this by opting in on the informed consent, portions of resected tissue will be delivered to the study neuropathologist, Dr. [name] or his designate, for histopathological analyses and to Dr. [name] or his designate for correlative molecular analyses. Tissue will be processed and stored in the Brain Tumor Biorepository at Duke (Duke IRB Pro0007434). Samples are assigned a patient de-identified biorepository number. The Biorepository database is Duke IRB-approved, accessible by Biorepository personnel only, and includes relevant data associated with the sample, such as Biorepository number, treatment with PVSRIPO, dates related to the sample, diagnosis, age, race, gender, pathology, and any other relevant information. Samples from tissue collected and stored for the aforementioned purpose may be analyzed within Duke at the request of the study investigators or may be sent to outside collaborators for analysis. Samples will always be identified by Biorepository number and/or Study ID number. Investigators will submit any such requests to the Biorepository using their internal tissue request form. Additional pathology analyses may include, but is not limited to, EGFRvIII and EGFRwt status, TERT, IDH 1 and 2, and MGMT IHC and MGMT promoter methylation, if a sufficient amount of tissue remains after standard clinical pathologic testing.

Tissue that is processed and stored by the Brain Tumor Biorepository for this study will be maintained indefinitely in the Biorepository for future testing until such time as the tissue supply designated for research is exhausted.

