15.7 Other Exploratory Objectives

An additional exploratory objective is to describe changes in tumor volume based upon imaging. Subjects' MRIs will be followed for changes in tumor volume post-PVSRIPO treatment. Another exploratory objective is the assessment of immunologic changes stemming from the administration of PVSRIPO treatment. Peripheral blood will be collected at defined intervals for correlative immune monitoring studies in serum and in peripheral blood monocytes. These include (i) analyses of innate and inflammatory immune events (HMGB1, inflammatory cytokines, NK and NKT-cells and regulatory immune subsets (Tregs & MDSCs)); (ii) analyses of adaptive immune responses (lineage, maturation, induction and activation/functional status of tumor antigen-specific T-cells). A final exploratory objective is to identify genetic predictors of response or failure of response to treatment with PVSRIPO. The Cox model will explore the impact of genetic markers of survival time. With logistic regression, the association between genetic markers and being a long-term survivor will be explored.

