15.9 Sample Size Calculation

A maximum of 12 patients will be treated on this study.

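### Section 15.7 seeks genetic predictors in at most 12 patients with Cox and logistic models that often give no finite estimate or miss their nominal level, and sets no marker list or multiplicity limit

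*Combined protocol and SAP*

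**What the plan says.** Section 9.1.4 takes tissue before infusion. After the clinical sample, "up to three additional core biopsies will be obtained, if possible". On their use it says: "They will be used for genetic analysis, including full genome or full exome sequencing as well as other molecular genetic testing". The scope is left open: "The molecular genetic testing will include, but is not limited to, DNA sequencing, gene amplification, and gene expression".

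Section 15.7 gives the aim: "A final exploratory objective is to identify genetic predictors of response or failure of response to treatment with PVSRIPO". Two models follow. A Cox model is to explore markers against survival time. For the binary outcome, "With logistic regression, the association between genetic markers and being a long-term survivor will be explored". Table 1 (Section 8) lists this as an other exploratory objective, with the endpoint "Identification of genetic markers as predictors of response". Section 15.9 sets the size: "A maximum of 12 patients will be treated on this study".

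For this analysis the plan gives no marker list, significance level, multiplicity limit or small-sample method, and no definition of a long-term survivor.

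**The concern.** Logistic and Cox regression rest on large-sample theory, and 12 patients is far from that. If any cell of the 2x2 table of marker by outcome is empty, the maximum-likelihood odds ratio is zero or infinite and its Wald p-value says nothing. The Cox score and likelihood-ratio tests can reject too often.

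A second problem is separate from the choice of model. Sequencing can supply a very large number of candidate markers, and nothing in the plan limits how many enter the models or how chance findings are handled.

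What is at stake is whether this objective, for which children give extra core biopsies, can return an interpretable answer, and whether a chance association is reported under an endpoint worded as identification.

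**Working it through.** The plan states no error rate or power for this analysis, so there is no figure to reproduce.

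**Inputs from the plan:** at most 12 patients (15.9); Cox and logistic models (15.7). **Assumed, because the plan is silent:** a binary marker unrelated to outcome; carrier frequency q of 10-30%, with 50% as a wider case; K = 1, 2 or 3 long-term survivors; a two-sided 5% level per marker.

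**1. Is the odds ratio finite?** It is finite only if all four cells are filled. Among markers that vary:

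P(not finite) = 1 - [1-(1-q)^K-q^K] x [1-(1-q)^(12-K)-q^(12-K)] / [1-(1-q)^12-q^12]

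For K = 3 and q = 0.2: 1 - 0.480 x 0.866 / 0.931 = 0.55. With K = 1 the first bracket is 0, so the result is 100%.

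| Long-term survivors | q = 10% | q = 20% | q = 30% |
|---|---|---|---|
| 3 | 77% | 55% | 39% |
| 2 | 84% | 69% | 59% |
| 1 | 100% | 100% | 100% |

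If survivor status is itself random (10-50%) and q runs from 10% to 50%, the range is 12% to 91%. The low end needs a common marker and an even outcome split. At 20% for both it is 67% with 12 patients and 80% with 8; fewer than 12 may have sequencing tissue.

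**2. Logistic tests at nominal 5%** (exact enumeration, q 20-50%, survivors 10-50%, markers that can be fitted). Wald rejects 0-1.1% of the time; likelihood ratio 4.9-9.0%. Wald also misses real effects: with half the patients carriers and long-term survival of 10% versus 60%, its power is 4%.

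**3. Cox tests at nominal 5%** (simulation, 20,000 null data sets per frequency, all 12 deaths observed, markers that vary):

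| Test | q = 10% | 20% | 30% | 50% |
|---|---|---|---|---|
| Score | 13.2% | 9.9% | 8.6% | 7.4% |
| Likelihood ratio | 12.6% | 9.1% | 7.6% | 6.7% |
| Wald | 2.2% | 3.4% | 4.2% | 4.9% |

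At q = 10%, 0.9^12 = 28% of markers have no carrier. Counting those as non-rejections, the score rate is 0.132 x 0.718 = 9.5%. A non-finite hazard ratio occurs in about 1-10% of data sets when nearly all deaths are observed. It rises to 41% with about 6 deaths and q = 10%.

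**4. Multiplicity, taking a test that holds exactly 5%.** The chance of at least one false positive among 20 independent null markers is 1 - 0.95^20 = 64%. If a share s of the screened markers is truly associated:

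false share of significant results = 0.05(1-s) / [0.05(1-s) + s x power]

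With 10 deaths and balanced carriers, power is 42% for a hazard ratio of 0.33 and 72% for 0.20. The false share is 99% at s = 0.1%, 87-92% at 1%, 38-52% at 10% and 22-32% at 20%. It passes one half when s falls below 0.05/(0.05 + power), that is 0.05/0.77 = 6% to 0.05/0.47 = 11%.

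**5. Can a wide screen be corrected?** The smallest two-sided Fisher p is 1/12 = 0.083 for K = 1, 1/66 = 0.015 for K = 2, 1/220 = 0.0045 for K = 3, and 1/792 = 0.0013 at best (K = 5). Bonferroni at 5% therefore allows at most 0.05 x 792 = 39 binary markers, 11 with K = 3, 3 with K = 2 and none with K = 1. For an assumed 20,000 genes the required p is 0.0000025.

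**The case against.** The text says explore, not test. It states no significance level and no p-value, does not specify unpenalised maximum likelihood, and nowhere says that every variant enters a model. Section 9.1.4 describes the assay, not the model inputs. Amplification and expression need not be binary, so steps 1 and 5 do not cover them. The objective is exploratory. All of this stands, and it limits the severity.

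Four stronger readings are tempting, and the documents do not support them:

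- *The models themselves make most reported predictors false.* The false share comes from unselected screening and low power, and would be about as high with an exact 5% test. Wald tests err the other way. For a short list with 20% true markers, most hits would be real under the assumptions of step 4.
- *More than a thousand false hits will follow.* This needs an assumed 20,000 genes and score or likelihood-ratio tests. At the Cox Wald rates, 20,000 x 0.022 to 0.049 gives 440 to 980.
- *False markers will steer patient selection in a later trial.* Nothing in the plan says these results will be used that way.
- *The plan already names a usable panel.* Section 9.1.4 does mention "EGFRvIII and EGFRwt status, TERT, IDH 1 and 2, and MGMT IHC and MGMT promoter methylation", but in the paragraph on opt-in tissue from later resections outside the protocol, as tests that may be done if tissue remains. Only patients who survive to resection would have such data, which would bias survival associations.

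The exploratory label does not answer the core point. An infinite odds ratio informs no one, and identification is a stronger word than these data can bear.

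**Conclusion.** The concern holds in a limited form. At 12 patients the named logistic model often has no finite estimate: 39-77% of varying binary null markers with 3 long-term survivors, 59-84% with 2, all with 1, at carrier frequencies of 10-30%. Wald logistic tests almost never reject. Cox score and likelihood-ratio tests reject about 7-13% at nominal 5% with all deaths observed, and Wald 2-5%. As a separate matter, if markers are screened without selection or a multiplicity limit, and few are truly associated, most nominally significant results would be false whichever test is used. A genome-wide screen of binary markers cannot be corrected at this size.

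The carrier frequencies, survivor counts, death counts and number of markers are assumptions, because the plan gives none. Severity is low: no primary, secondary or stopping decision depends on this objective.

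**What to change.** In Section 15.7:

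- Name a short list of markers, measured on the pre-infusion biopsy and fixed before outcome data are examined. Do not use later-resection tissue for it.
- Define a long-term survivor by a time point already in the plan, such as alive at 24 months (Table 1, Section 15.5), and say how patients with shorter follow-up are handled.
- Replace ordinary logistic regression with Fisher's exact test or exact or Firth-penalised logistic regression.
- Replace asymptotic Cox tests with a permutation log-rank test, plus Firth-penalised Cox estimates with profile-likelihood intervals.
- State how many markers are examined and label the results hypothesis-generating. If an adjusted claim is wanted from Fisher's test, step 5 caps the list at 3 markers with 2 survivors and 11 with 3.
- Report the remaining sequencing as a per-patient listing without p-values.

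In Table 1, reword the endpoint as a description of the association of named markers with survival.

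The cost is protocol wording and standard software, with no change to patients, visits or sample size. The downside is wide intervals and fewer reported associations. Exact and penalised methods make the estimates usable; they do not make a wide screen workable.
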